7.3.4. Characterize Quality of Life (QOL)

Data from the QoL instruments will be collected to assess kidney disease specific measures. Analyses of these instruments will be performed on the Safety Analysis Set. The instrument used is based upon the age of the patient at screening; for each patient, the instrument selected based on age at screening will be used consistently throughout the study. [Table 1](#) outlines the QoL instruments to be used based upon age at screening.

Table 1: QOL Instruments by Age at Screening in Study 002 (<18 years vs ≥18 years)

Age at Screening	QOL Instruments	Domains/Subscales	Notes
≥18 years of age	KDQOL-36	5 subscales: SF-12 Physical Component Score, SF-12 Mental Component Score, Symptoms/Problems, Effects of Kidney Disease and Burden of Kidney Disease	
<18 years of age	PedsQL and ESRD model	
PedsQL: 4 multi-dimensional scales: Physical Functioning, Emotional Functioning, Social Functioning and School Functioning
 
3 summary scores (total score, physical health summary score and psychosocial health summary score).
 
ESRD: 7 domains: General Fatigue, About My Kidney Disease, Treatment Problems, Family and Peer Interaction, Worry, Perceived Physical Appearance, and Communication.
 
Total Score
	No common variables.

For each instrument, descriptive statistics will be generated at baseline and each post-baseline scheduled visit. For the PedsQL, both parent and/or child may complete the questionnaire. Summary statistics at each visit for each subscale/score will summarize responses separately based upon the parent and child responses.

7.3.5. Incidence of ADA

The number and associated percentage of patients who are ADA positive at baseline and at any post-baseline visit will be summarized. A listing of patients with ADA positivity with their associated titer value AEs will also be provided.

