2.3. Exploratory Objectives

- Characterize the pharmacokinetics (PK) of ALN-GO1
- Evaluate the PD effect of ALN-GO1 on urinary glycolate excretion, plasma oxalate concentration, plasma glycolate concentration, and urine oxalate:creatinine ratio
- Evaluate the incidence of anti-drug antibodies (ADA)

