4.3. Number of Patients

Up to 20 patients are planned for enrollment in this study.

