8.2.7. Anti-drug Analyses

Anti-drug antibody results will be summarized descriptively. A by-patient data listing will also be provided.

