8.2.8. Safety Analyses

Extent of exposure will be summarized. Adverse events will be summarized by the Medical Dictionary for Regulatory Activities (MedDRA) System Organ Class (SOC) and Preferred Term. Prior and concomitant medications will be classified using an internationally recognized and accepted coding dictionary.

Incidence of AEs (those events that started after exposure to study drug or worsened in severity after dosing) will be presented. Incidence of AEs will also be presented by maximum severity and relationship to study medication. The incidence of SAEs and AEs leading to discontinuation of treatment will also be tabulated. By-patient listings will be provided for deaths, SAEs, and events leading to discontinuation of treatment. Additional tabular summaries of AEs may be presented by other grouping including, but not limited to high level term (HLT), high level group term (HLGT), or standardized MedDRA query (SMQ).

Descriptive statistics will be provided for clinical laboratory data and vital signs data, presented as both actual values and changes from baseline relative to each on-study evaluation and to the last evaluation on study. Laboratory shift tables from baseline to worst values will be presented. Abnormal physical examination findings, renal ultrasound, ECG, and echo data will be presented in by-patient listings.

Descriptive statistics will be provided for electrocardiogram interval data and presented as both actual values and changes from baseline relative to each on-study evaluation and to the last evaluation on study. Details of any abnormalities will be included in patient listings.

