3.2.3. Exploratory Endpoints

- Describe the effect of lumasiran on other safety parameters, including assessments of vital signs, electrocardiograms (ECG), renal ultrasounds, clinical laboratory parameters, and physical examinations
- Assess lumasiran plasma PK parameters including maximum plasma concentration (C_{max}), time to maximum plasma concentration (t_{max}), elimination half-life, area under the curve, fraction of dose excreted in urine, apparent clearance and apparent volume of distribution.
- Change from baseline over the course of the study in the following PD parameters: urinary glycolate excretion, plasma oxalate concentration, plasma glycolate concentration and urine oxalate:creatinine ratio
- Quality of life as assessed by Kidney Disease Quality of Life Questionnaire (KDQOL) for adults (≥ 18 years of age) and the PedsQOL (the generic and ESRD modules) for children (< 18 years of age)
- Incidence of ADA

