5.3. Baseline Definitions

Baseline will be defined as the derived baseline value in Study ALN-GO1-001 (refer to SAP ALN-GO1-001, Version 2.0; dated August 13, 2018). For data not collected in the parent study (e.g. KDQOL-36, PedsQOL, Renal Ultrasounds), the baseline value will be defined as the latest collection prior to the first dose of lumasiran in this study.

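### The planned anti-drug antibody table does not separate new positives from patients already positive at baseline, so it need not give the incidence named as the endpoint

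*SAP*

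**What the plan says.** Both documents name incidence as the quantity of interest. It is an exploratory objective in Protocol 2.3 and SAP 3.1.3, and SAP 3.2.3 lists the endpoint as "Incidence of ADA".

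The only planned table is in SAP 7.3.5: "The number and associated percentage of patients who are ADA positive at baseline and at any post-baseline visit will be summarized". The same section adds a listing: "A listing of patients with ADA positivity with their associated titer value AEs will also be provided". Protocol 8.2.7 says "Anti-drug antibody results will be summarized descriptively" and also promises a data listing by patient.

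On the reference point, SAP 5.3 states: "Baseline will be defined as the derived baseline value in Study ALN-GO1-001". For data that the parent study did not collect, it falls back to the last value before the first dose in this study.

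For adverse events, Protocol 8.2.8 ties the word incidence to onset or worsening: "Incidence of AEs (those events that started after exposure to study drug or worsened in severity after dosing) will be presented". SAP 7.1.1 likewise defines a treatment-emergent event. ADA has no matching rule.

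**The concern.** An incidence counts patients who become positive among those who could. The planned post-baseline row counts everyone with a positive sample at any later visit, including a patient who was positive at baseline and simply stayed positive. The section defines neither new nor boosted ADA, does not restrict the denominator to patients at risk, and does not cross-classify baseline status by later status.

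In an extension study the choice of baseline adds to this. If ADA was sampled in the parent study, a patient who turned positive there and is still positive here appears in the post-baseline row, and the table does not show in which study the antibody arose. If ADA was not sampled there, the baseline sample itself follows earlier lumasiran dosing, so a positive baseline need not be pre-existing reactivity. SAP 7.3.5 does not say which case applies, or whether the pre-dose sample in this study counts as post-baseline.

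At stake is how the immunogenicity of long-term dosing is described in the report. No hypothesis test or decision rule in these documents depends on it.

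**Working it through.** The documents state no ADA rate, so there is no planned figure to reproduce. The check is whether the two planned counts fix the number of new positives.

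**Inputs**
- N = 20, the maximum enrolment (Protocol 4.3: "Up to 20 patients are planned for enrollment in this study").
- B = number positive at baseline; P = number positive at one or more later visits. The documents give neither, so both are assumed over a range.
- Every patient is assumed to have a baseline and a later sample.

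**Formulas**
- Let A be the number positive at both times. New positives = P − A.
- A can be no larger than the smaller of B and P, and no smaller than max(0, P + B − N).
- So new positives lie between max(0, P − B) and min(P, N − B).
- Planned percentage = P/N. Incidence proportion = new positives/(N − B).

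**Results at N = 20**

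| B | P | Planned baseline row | Planned post-baseline row | New positives | Incidence proportion |
|---|---|---|---|---|---|
| 0 | 3 | 0.0% | 15.0% | 3 of 20 | 15.0% |
| 1 | 1 | 5.0% | 5.0% | 0 to 1 of 19 | 0% to 5.3% |
| 1 | 3 | 5.0% | 15.0% | 2 to 3 of 19 | 10.5% to 15.8% |
| 2 | 2 | 10.0% | 10.0% | 0 to 2 of 18 | 0% to 11.1% |
| 2 | 3 | 10.0% | 15.0% | 1 to 3 of 18 | 5.6% to 16.7% |
| 3 | 3 | 15.0% | 15.0% | 0 to 3 of 17 | 0% to 17.6% |

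Worked line for B = 3, P = 3: the lower bound is max(0, 3 − 3) = 0, the upper bound is min(3, 17) = 3, and 3/17 = 17.6%. The plan would print 15.0% in both rows whether every later positive was persistent or every one was new.

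The first line is the exception. With B = 0 there is nobody to persist, A = 0, and P/N is the cumulative incidence proportion from that baseline.

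As a count, the post-baseline row exceeds the number of new positives by exactly A. As a percentage the gap can go either way, because the denominators differ: if all 3 later positives are new, 15.0% lies below 17.6%; if none is, 15.0% stands against 0%.

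**The case against.** The strongest reply is that little is lost. The endpoint is exploratory and descriptive. With at most 20 patients, the ADA listings in Protocol 8.2.7 and SAP 7.3.5 should let a reader work out new positives patient by patient. That stands as a real mitigation. It is partial, because a listing is not a planned endpoint summary, the SAP sentence on it is garbled where titre and adverse events run together, and neither document says that the listing will show parent-study results.

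A reader might also infer more than the text supports:

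- **That pre-existing positivity goes unreported.** It does not: baseline positives get their own count. Only the split of the later positives is missing.
- **That the sentence counts only patients positive at both times.** The grammar allows this, but SAP 7.2.1 and 7.3.4 use very similar phrasing for separate time points, and a both-times count would make no sense under this section's title.
- **That the planned figure can never be an incidence.** With no baseline positives it is one.
- **That each baseline positive adds 5 percentage points (1/20).** It adds to the later count only if that patient is positive again after baseline.
- **That patients who turned positive in the parent study are miscounted.** This presumes ADA sampling in the parent study, which these documents do not confirm. Against a pre-lumasiran baseline, such a patient is a genuine treatment-emergent case. Showing the two studies separately makes the table more informative but does not correct an error.

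**Conclusion.** The point holds as a gap in one exploratory table. As written, SAP 7.3.5 does not deliver the endpoint it is headed with unless no patient is positive at baseline. Otherwise the later percentage can mix persistent and new positives, and the two counts leave the number of new positives undetermined: in the 3-and-3 example, anywhere from 0% to 17.6% behind a reported 15.0%.

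The size is illustrative. It rests on assumed counts, on the maximum of 20 patients, and on complete sampling. The documents give no baseline positivity rate, so how often the problem would arise is unknown. Whether the parent-study value or this study's pre-dose value serves as ADA baseline is also open, because SAP 5.3 makes it conditional and the parent study's SAP is not available here. Not every part of the SAP was available for checking; no rule for new ADA appears in the text that was.

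The primary safety endpoint and the secondary endpoints are not affected. This is a low-severity improvement worth making because it is nearly free.

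**What to change.** Amend SAP 7.3.5 as follows:

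1. Keep baseline prevalence as its own row.
2. Report new ADA: patients negative at baseline who become positive, over baseline-negative patients with at least one post-dose sample.
3. If boosted responses are wanted, prespecify the titre rise and report them on a separate row, over baseline-positive patients.
4. Add a cross-table of baseline by post-baseline status.
5. State the ADA baseline: the pre-lumasiran value from the parent study if ADA was sampled there; otherwise the last sample before the first dose in this study, labelled as following earlier lumasiran exposure.
6. State whether the pre-dose sample in this study counts as post-baseline.
7. Where parent-study ADA data exist, show first positivity in the parent study and in this study separately.

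The cost is SAP wording and one table shell. No new sampling is needed in this study. Item 7 depends on whether the parent study holds ADA data.
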